### 9.2.2.2 *Analysis of the Key Secondary Estimand*

Progression to intubation or death will be analysed using the same methods as progression to severe disease or death, as detailed in [Section 9.2.1.2](#).

### 9.2.2.3 *Sensitivity Analyses of the Key Secondary Estimand*

The sensitivity to missing data will be assessed in the same way as described for progression to severe disease or death in [Section 9.2.1.3](#).

#### 9.2.2.3.1 *Sensitivity to the Severe Disease Definition*

The following analyses will explore different subsets of the progressed population:

- A sensitivity analysis which will only consider OSCi assessments between Day 6 and Day 35 for the derivation of progression to intubation or death. The purpose of this analysis is to assess the rate of progression after a sufficient period of time has passed for the study drug to have a beneficial effect. Patients who die prior to Day 6 will be excluded from the analysis.
- A sensitivity analysis which will exclude short term progressions. Short term progressions are defined by OSCi scores of  $\geq 6$  which are not maintained for consecutive scheduled assessments.
- A summary of patients with a maximum OSCi score of 6. This summary will assess patients who progress to intubation but who do not progress to additional organ support.
- A summary of patients who progress to intubation but are subsequently discharged from hospital.
- A summary of patients who progress to intubation but subsequently recover.

### 9.2.2.4 *Supportive Estimands*

A supportive estimand for the key secondary endpoint will be defined as follows. The difference in probabilities for SNG001 versus placebo for progression to intubation or death within 35 days of first dose will be estimated for the per protocol population. Reasons for excluding patients from the PP population are described in [Section 7.1.2](#). Of note, many of the reasons are based on assessments prior to randomisation and treatment and so the exclusions are independent of treatment. Intercurrent events will be handled as per table 18.

**Table 18: Intercurrent events and policies for the supportive estimand of progression to intubation or death**

Intercurrent event	Policy
Death	Composite variable: The definition of the endpoint includes patients who die within 35 days of first dose, regardless of their OSCi assessments.
Missed 2 of the first 3 scheduled doses	Hypothetical (estimand for a situation with treatment compliance): OSCi assessments will be considered missing if two doses or more of the randomised treatment were missed within the first three days of therapy, with the corresponding patients excluded from the PP analysis set. A single dose within the first three scheduled dosing days is not expected to be sufficient for the study drug to be effective, therefore this

## Statistical Analysis Plan (RotW)

Final v1.0, 08FEB2022

SG018

	approach will help establish the true treatment effect. It is assumed that such exclusions are not related to treatment.
Other premature treatment discontinuation and missed doses	Treatment policy: Intubation will be determined regardless of treatment discontinuation and the number of missed doses (other than missing 2 out of the first 3 scheduled doses).
Withdrawal from study	While-on-study: Patients will only be considered as intubated if observed and recorded whilst participating in the study. This assumes the treatment effect is independent to reason for study withdrawal.
Other protocol deviations affecting efficacy	Hypothetical (estimand for a situation with no protocol deviations affecting efficacy): To establish the true treatment effect all OSCI assessments will be considered missing if protocol deviations affecting efficacy are recorded on or prior to Day 35.
Medications affecting efficacy	Treatment policy: Intubation will be determined regardless of any concomitant medication use.

A second supportive estimand will estimate the difference in probabilities for SNG001 versus placebo for progression to intubation or death within 35 days of first dose in the per protocol population who do not receive medications affecting efficacy. Medications affecting efficacy will be defined as COVID-19 therapies which are approved for use (including emergency use) at the time of the primary analysis and will be handled as per table 19.

**Table 19: Intercurrent events and policies for the second supportive estimand of progression to intubation or death**

Intercurrent event	Policy
Death	Composite variable: The definition of the endpoint includes patients who die within 35 days of first dose, regardless of their OSCI assessments.
Missed 2 of the first 3 scheduled doses	Hypothetical (estimand for a situation with treatment compliance): OSCI assessments will be considered missing if two doses or more of the randomised treatment were missed within the first three days of therapy, with the corresponding patients excluded from the PP analysis set. A single dose within the first three scheduled dosing days is not expected to be sufficient for the study drug to be effective, therefore this approach will help establish the true treatment effect. It is assumed that such exclusions are not related to treatment.

Other premature treatment discontinuation and missed doses	Treatment policy: Intubation will be determined regardless of treatment discontinuation and the number of missed doses (other than missing 2 out of the first 3 scheduled doses).
Withdrawal from study	While-on-study: Patients will only be considered as intubated if observed and recorded whilst participating in the study. This assumes the treatment effect is independent to reason for study withdrawal.
Other protocol deviations and prior medications affecting efficacy	Hypothetical (estimand for a situation with no protocol deviations or prior medications affecting efficacy): To establish the true treatment effect all OSCI assessments will be considered missing if protocol deviations affecting efficacy are recorded on or prior to Day 35 or medications affecting efficacy are being received at the time of first dose.
Concomitant medications affecting efficacy	Composite: Only assessments prior to the first dose of any medication affecting efficacy will be considered for the derivation of intubation.

#### 9.2.2.5 Analysis of the Supportive Estimands

The supportive estimand of progression to intubation or death will be analysed using the same methods as progression to severe disease or death, as detailed in [Section 9.2.1.2](#).

### 9.2.3 Death

#### 9.2.3.1 Key Secondary Estimand

The key secondary estimand will be the difference in probabilities for SNG001 versus placebo for death within 35 days of first dose of patients in the ITT population. Intercurrent events will be handled as per Table 20.

**Table 20: Intercurrent events and policies for the key secondary estimand of death**

Intercurrent event	Policy
Premature treatment discontinuation and missed doses	Treatment policy: Death will be determined regardless of treatment discontinuation and the number of missed doses.
Withdrawal from study	While-on-study: Deaths which occur after study withdrawal will not be considered, unless consent is received to include death details in the clinical study database. This assumes the treatment effect is independent to reason for study withdrawal.
Other protocol deviations and concomitant medications affecting efficacy	Treatment policy: Death will be determined regardless of any concomitant medication use or protocol deviations.

**9.2.3.2 Analysis of the Key Secondary Estimand**

Death will be analysed using the same methods as progression to severe disease or death, as detailed in [Section 9.2.1.2](#).

**9.2.3.3 Sensitivity Analyses of the Key Secondary Estimand**

The sensitivity to missing data will be assessed in the same way as described for progression to severe disease or death in [Section 9.2.1.3](#).

**9.2.3.3.1 Sensitivity to the Severe Disease Definition**

The following analyses will explore different subsets of the progressed population:

- A sensitivity analysis which will only consider OSCI assessments between Day 6 and Day 35 for the derivation of death. The purpose of this analysis is to assess the rate of mortality after a sufficient period of time has passed for the study drug to have a beneficial effect.

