8.5.5 Handling of Missing Data

For analyses using the WHO OSCI, including the primary and key secondary endpoints, patients with a WHO OSCI score of 8, indicating death, will have any subsequent missing WHO OSCI assessments imputed as 8. In addition, if other data sources such as AEs indicate a patient has died all missing WHO OSCI scores on and after the date of death will be imputed as 8.

For relevant analyses, missing WHO OSCI assessments for patients who withdraw from the study alive will be imputed using multiple imputation under a missing at random assumption. Selected analyses will be repeated using a missing not at random approach through an imputation model estimated from patients in the placebo group.

For the mixed models with repeated measures (MMRM) of breathlessness, missing breathlessness scores will be imputed as 4 if the WHO OSCI score at the corresponding visit is ≥ 5 . Cough and sputum scores at corresponding visits will be considered missing at random and total BCSS scores will be calculated by summing the imputed symptom scores, where possible. Missing breathlessness, cough and sputum scores at all other visits will be considered missing at random and will not explicitly be imputed but will be accounted for by the MMRM analysis. Missing not at random approaches may also be considered for sensitivity analyses.

Further details regarding missing data approaches will be given in the SAP.

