#### 5.3.1.5 *Death within 35 days of First Dose or Randomisation*

Deaths will be identified by an OSCi score of 8 at any post baseline assessment up to and including Day 35, a fatal Adverse Event (AE) on or before Day 35 or withdrawal due to a fatal AE on or before Day 35.

Patients who die after Day 35 will be considered alive for the derivation of death within 35 days of first dose or randomisation.

Day 35 will be determined by the study schedule, which may be more than 35 days after randomisation if randomisation occurs before Day 1.

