## 7.3 Missing Data

### 7.3.1 OSCi

#### 7.3.1.1 General Imputation Rules

For analyses using the OSCi, including the primary and key secondary endpoints, subjects with an OSCi score of 8, indicating death, will have any subsequent missing OSCi assessments set as 8. In addition, if other data sources such as AEs indicate a patient has died all missing OSCi scores on and after the date of death will be set as 8. Any missing baseline OSCi scores will be imputed as 4, as per the study inclusion criteria.

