#### 9.2.1.3.1 *Sensitivity to the Severe Disease Definition*

The following analyses will explore different subsets of the progressed population:

- A sensitivity analysis which will only consider OSCi assessments between Day 6 and Day 35 for the derivation of progression to severe disease or death. The purpose of this analysis is to assess the rate of progression after a sufficient period of time has passed for the study drug to have a beneficial effect. Patients who die prior to Day 6 will be excluded from the analysis.
- A sensitivity analysis which will exclude short term progressions. Short term progressions are defined by OSCi scores of  $\geq 5$  which are not maintained for consecutive scheduled assessments.
- A summary of patients with a maximum OSCi score of 5. This summary will assess patients who progress to non-invasive or high flow oxygen but who do not progress to intubation.
- A summary of patients who progress to severe disease but are subsequently discharged from hospital.
- A summary of patients who progress to severe disease but subsequently recover.

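### The Day 6–35 sensitivity analysis of death does not exclude deaths before Day 6, so as written it repeats the main death analysis

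*SAP*

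**What the plan says.** The SAP has three sensitivity analyses limited to Days 6 to 35, one for each key secondary endpoint.

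- **Death (SAP 9.2.3.3.1).** The plan is "A sensitivity analysis which will only consider OSCI assessments between Day 6 and Day 35 for the derivation of death". The purpose is "to assess the rate of mortality after a sufficient period of time has passed for the study drug to have a beneficial effect". Nothing is said about patients who die before Day 6.
- **Severe disease or death (SAP 9.2.1.3.1) and intubation or death (SAP 9.2.2.3.1).** The window is the same, and both sections add: "Patients who die prior to Day 6 will be excluded from the analysis".

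Three derivation rules bear on these analyses.

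- **Scores after death (SAP 7.3.1.1).** For analyses using the ordinal scale, key secondary endpoints included, patients with a score of 8 "will have any subsequent missing OSCi assessments set as 8". Deaths known from elsewhere, such as from adverse event records, are treated alike: missing scores from the day of death onwards also become 8. Protocol section 8.5.5 agrees: such patients "will have any subsequent missing WHO OSCI assessments imputed as 8".
- **Death endpoint (SAP 5.3.1.5).** "Deaths will be identified by an OSCi score of 8 at any post baseline assessment up to and including Day 35", or by a fatal adverse event in that period. The 8 need not be the first one.
- **Progression endpoints (SAP 5.3.1.3 and 5.3.1.4).** Any post-baseline score at or above 5, or at or above 6, counts. The only exclusion for earlier severity concerns the baseline score.

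**The concern.** The death analysis is meant to separate late mortality from deaths too early for the drug to have prevented. Restricting which daily scores are read does not achieve this when a death on Day 3 puts an 8 on every later day. The sentence that would deal with it appears in the two sibling analyses but not here.

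At stake is interpretation. A reader who sees a Day 6–35 mortality result agree with the main result could take it as separate support. In fact it would be the same result, and a delayed effect, which this analysis is there to reveal, would stay hidden.

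A second, smaller question concerns the two progression versions. They read status within the window, so a patient who reached the threshold before Day 6 and is still there on Day 6 is counted, although the progression began earlier.

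**Working it through.** The documents state no event count, power or rate for these analyses, so there is no planned figure to reproduce. The check applies the rules to constructed patients and then illustrates the size.

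**Step 1: the rules applied.** An event is any score at or above the threshold on Days 6–35. The score 8 is carried forward after death. Deaths before Day 6 are excluded only where the SAP says so.

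| Patient | Severe disease or death | Intubation or death | Death |
|---|---|---|---|
| A: dies Day 3 | excluded | excluded | **event** |
| B: dies Day 10 | event | event | event |
| C: score 5 on Days 3–8, then improves | **event** (first reached Day 3) | no event | no event |
| D: score 5 on Days 3–4 only | no event | no event | no event |
| E: first score 5 on Day 8 | event | no event | no event |
| F: score 6 on Days 4–9 | **event** (first reached Day 4) | **event** (first reached Day 4) | no event |
| G: never reaches 5 | no event | no event | no event |

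Patient A is the main point. Every death up to Day 35, early or late, leaves an 8 inside the window. The deaths counted and the patients analysed are then the same as in the main analysis.

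**Step 2: the other reading.** If the carried-forward 8 is held not to be an assessment, patient A has no score of 8 in the window and becomes a non-event. A patient who died on Day 3 is then counted as a survivor in the denominator.

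**Step 3: illustration of size.** Assumptions, none from the documents:

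- placebo 35-day mortality p of 5% or 10%;
- a share s of placebo deaths before Day 6 of 10%, 20% or 40%;
- no drug effect before Day 6 and a risk ratio of 0.60 from Day 6.

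The arm size of 305 is from SAP section 6.

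With early deaths counted, risk ratio = s + 0.60 × (1 − s), whatever p is:

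- s = 10%: 0.10 + 0.54 = 0.64
- s = 20%: 0.20 + 0.48 = 0.68
- s = 40%: 0.40 + 0.36 = 0.76

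These are also the main-analysis values. With early deaths excluded from both arms, the ratio returns to the assumed 0.60.

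Early deaths per placebo arm = 305 × p × s. The range is 305 × 0.05 × 0.10 = 1.5 to 305 × 0.10 × 0.40 = 12.2.

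Under the reading in step 2, with p = 10% and s = 40%, placebo late mortality would be 0.06 / 1 = 6.0%. Among patients alive at Day 6 it is 0.06 / 0.96 = 6.25%. The ratio stays at 0.60 here only because early mortality is assumed equal in the arms. Otherwise the arm with more early deaths carries more dead patients as survivors.

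**The case against.** **The intent of the death analysis is clear.** The window limits which assessments are used, the fill-in rule creates values and not assessments, and a programmer who reads the stated purpose would not count a Day 3 death. The missing sentence is most plausibly a drafting omission. That is fair as to intent. But section 7.3.1.1 applies expressly to key secondary analyses, and dropping the fill-in turns early deaths into survivors. Neither reading gives the stated quantity.

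**Status from Day 6 is a coherent outcome for the progression versions.** The main endpoints are status-based, and neither section asks for new or first events. The analysis drops brief early progression (patient D) and keeps patients who remain severe. This stands: counting patients C and F is an error only if first onset was intended. The stated aim, a progression rate after the drug has had time to act, leans that way but does not settle it. What remains is a labelling need.

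**A first-onset analysis has its own costs.** It conditions on what happened after randomisation, and it loses late deaths among early progressors. A patient at 5 on Day 3 who dies on Day 20 would leave the severe-disease analysis. This also stands.

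**Stronger readings that the documents do not support.**

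- A reader might infer that all three analyses re-count early deaths. The two progression versions exclude them.
- A reader might describe the early progressors as ventilated. A score of 5 also covers high-flow oxygen (protocol section 6.6).
- A reader might expect the result to be presented as evidence on late mortality. That is a guess from the stated purpose.

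**Conclusion.** The point holds for the death analysis. Followed as written, it counts deaths before Day 6 and repeats the main death analysis. This rests on reading together SAP sections 9.2.3.3.1, 7.3.1.1 and 5.3.1.5, not on any assumed rate. The size is not known from the documents: 0.64 to 0.76 against 0.60, and about 1.5 to 12 early deaths per arm, depend wholly on the assumptions above.

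For the two progression analyses the conclusion is limited: they measure status from Day 6 and should not be read as new progression.

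The matter is minor. These are sensitivity analyses outside the testing sequence in SAP section 7.6, and no primary or key secondary test is affected.

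**What to change.** 1. In SAP section 9.2.3.3.1, state that patients who die before Day 6 are excluded, as in the two sibling sections. Equivalently, define the event by date of death on Days 6–35 among patients alive at the start of Day 6.
2. Show the number of deaths before Day 6 by arm beside the result.
3. Label the result as conditional on survival to Day 6, and so not a fully randomised comparison.
4. In SAP sections 9.2.1.3.1 and 9.2.2.3.1, label the analyses as status from Day 6, and tabulate by arm the patients whose first event came before Day 6.
5. Optionally, add a first-onset version as a supplement, noting that it conditions on a post-randomisation state and drops late deaths among early progressors.

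The cost is a few lines of SAP text and small tables, with no new data. The price in interpretation is the conditioning in item 3, which the two sibling analyses already carry.

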**9.2.3.4 Supportive Estimands**

A supportive estimand for the key secondary endpoint will be defined as follows. The difference in proportions for SNG001 versus placebo for death within 35 days of first dose will be estimated for the per protocol population. Reasons for excluding patients from the PP population are described in [Section 7.1.2](#). Of note, many of the reasons are based on assessments prior to randomisation and treatment and so the exclusions are independent of treatment. Intercurrent events will be handled as per table 21.

**Table 21: Intercurrent events and policies for the supportive estimand of death**

Intercurrent event	Policy
Missed 2 of the first 3 scheduled doses	Hypothetical (estimand for a situation with treatment compliance): OSCI assessments will be considered missing if two doses or more of the randomised treatment were missed within the first three days of therapy, with the corresponding patients excluded from the PP analysis set. A single dose within the first three scheduled dosing days is not expected to be sufficient for the study drug to be effective, therefore this approach will help establish the true treatment effect. It is assumed that such exclusions are not related to treatment.
Other premature treatment discontinuation and missed doses	Treatment policy: Death will be determined regardless of treatment discontinuation and the number of missed doses (other than missing 2 out of the first 3 scheduled doses).
Withdrawal from study	While-on-study: Patients will only be considered as intubated if observed and recorded whilst participating in the study. This assumes the treatment effect is independent to reason for study withdrawal.
Other protocol deviations affecting efficacy	Hypothetical (estimand for a situation with no protocol deviations affecting efficacy): To establish the true treatment effect all OSCI assessments will be considered missing if protocol deviations affecting efficacy are recorded on or prior to Day 35.

## Statistical Analysis Plan (RotW)

Final v1.0, 08FEB2022

SG018

Medications affecting efficacy	Treatment policy: Death will be determined regardless of any concomitant medication use.
--------------------------------	--

A second supportive estimand will estimate the difference in probabilities for SNG001 versus placebo for death within 35 days of first dose in the per protocol population who do not receive medications affecting efficacy. Medications affecting efficacy will be defined as COVID-19 therapies which are approved for use (including emergency use) at the time of the primary analysis and will be handled as per table 22.

**Table 22: Intercurrent events and policies for the second supportive estimand of death**

Intercurrent event	Policy
Missed 2 of the first 3 scheduled doses	Hypothetical (estimand for a situation with treatment compliance): OSCI assessments will be considered missing if two doses or more of the randomised treatment were missed within the first three days of therapy, with the corresponding patients excluded from the PP analysis set. A single dose within the first three scheduled dosing days is not expected to be sufficient for the study drug to be effective, therefore this approach will help establish the true treatment effect. It is assumed that such exclusions are not related to treatment.
Other premature treatment discontinuation and missed doses	Treatment policy: Death will be determined regardless of treatment discontinuation and the number of missed doses (other than missing 2 out of the first 3 scheduled doses).
Withdrawal from study	While-on-study: Patients will only be considered as intubated if observed and recorded whilst participating in the study. This assumes the treatment effect is independent to reason for study withdrawal.
Other protocol deviations and prior medications affecting efficacy	Hypothetical (estimand for a situation with no protocol deviations or prior medications affecting efficacy): To establish the true treatment effect all OSCI assessments will be considered missing if protocol deviations affecting efficacy are recorded on or prior to Day 35 or medications affecting efficacy are being received at the time of first dose.
Concomitant medications affecting efficacy	Composite: Only assessments prior to the first dose of any medication affecting efficacy will be considered for the derivation of death.

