#### 7.3.1.3 Imputation Rules for Binary Endpoints

Key secondary analyses will use the available data. Therefore, for subjects who withdraw from the study prior to day 35 this assumes that any progression to severe disease, intubation or death can only occur prior to study withdrawal. This assumption will be tested by using multiple imputation methods to impute the missing data. Further details are given in [Section 9.2.1.3](#).

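### The second supportive estimands call start of approved COVID-19 therapy 'Composite' but only discard later data; in SAP Table 22 a death after therapy start is therefore scored as no death

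*SAP*

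**What the plan says.** SAP Sections 9.1.1.4, 9.1.2.4, 9.2.1.4, 9.2.2.4 and 9.2.3.4 each define a second supportive estimand "in the per protocol population who do not receive medications affecting efficacy". Each then refers to a table that has two medication rows.

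- **Prior medication.** In Table 22, all OSCI assessments are treated as missing if "medications affecting efficacy are being received at the time of first dose". The other four tables have the equivalent.
- **Concomitant medication.** In Table 22: "Composite: Only assessments prior to the first dose of any medication affecting efficacy will be considered for the derivation of death". Tables 16 and 19 use the same wording for severe disease and for intubation. Tables 10 and 13 right-censor the patient at the date before first use. All five rows carry the label 'Composite'.

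The other death estimands treat concomitant therapy differently. The ITT key secondary estimand (Table 20) has "Treatment policy: Death will be determined regardless of any concomitant medication use or protocol deviations", and the first supportive estimand (Table 21) has "Treatment policy: Death will be determined regardless of any concomitant medication use".

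Section 5.3.1.5 identifies deaths from an OSCI score of 8 and also from "a fatal Adverse Event (AE) on or before Day 35 or withdrawal due to a fatal AE on or before Day 35". Where other data show that a patient has died, Section 7.3.1.1 says "all missing OSCi scores on and after the date of death will be set as 8". On missing data, Section 7.3.1.3 says "Key secondary analyses will use the available data". The method for death is the logistic regression of Section 9.2.1.2, applied through Section 9.2.3.5.

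**The concern.** A composite strategy makes the intercurrent event part of the outcome. The SAP uses the term that way for death: Table 8 holds the patient at the maximum of 28 days, Table 14 counts death as the event, and Table 23 says a patient who dies cannot recover. For therapy start, the five second supportive tables do nothing of the kind, although Section 15 introduces these estimands partly because starting therapy may indicate that study treatment had not worked.

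The mismatch matters most for death. A pre-specified mortality analysis would record a known death, in a patient still under observation, as no death. If therapy is started more often in one arm, or more of one arm's deaths follow it, the treatment comparison shifts for a reason unrelated to mortality. In Tables 10 and 13 the programmer would have to choose between two censoring dates for the same patient.

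**Working it through.** **1. Table 22, one patient traced.** A patient starts approved therapy on Day 5 and dies on Day 12.

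- Assessments before Day 5 cannot show death, because the patient was alive when therapy started. Under the therapy row no usable assessment is a death. With a logistic model on available data, the result is a non-event.
- Under Section 5.3.1.5 the fatal AE makes the patient a death. Section 7.3.1.1 would set missing scores from Day 12 to 8, but those scores also fall after therapy start, where the therapy row discards them.
- Under the population sentence in Section 9.2.3.4 the patient would not be in the analysis.

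Table 22 has no Death row. That is natural where death is the endpoint (Tables 20 and 21 have none either), but it means nothing offsets the therapy row.

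**2. Tables 16 and 19.** Both have a Death row that counts deaths within 35 days whatever the OSCI assessments show, so the Day 12 death counts. What is lost is non-fatal severe disease or intubation after therapy start. The label is wrong here too.

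**3. Tables 10 and 13.** The Death row censors the same patient at Day 28. The therapy row censors at Day 4. No precedence is stated.

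**4. Size in Table 22.** The plan has no figure to reproduce, and every rate below is assumed. Let p be the risk of death by Day 35, f the share of deaths that follow therapy start, and t the share starting therapy.

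- All deaths counted: p
- Table 22 as written: p(1 - f)
- Starters excluded: p(1 - f)/(1 - t)
- Therapy start or death: t + p(1 - f)

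Arms are given as SNG001 v placebo, and differences as SNG001 minus placebo.

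*No true difference, unequal f.* Take p = 10% v 10% and f = 0.35 v 0.25. Counting all deaths gives 0. As written: 10 x 0.65 = 6.5% v 10 x 0.75 = 7.5%, a difference of -1.0 point. The odds ratio is (0.065/0.935)/(0.075/0.925) = 0.86. Reversing f gives +1.0 point and an odds ratio of 1.17.

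*True difference, equal f.* Take p = 5% v 10% and t = 20% in both arms.

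| f | All deaths | As written | Starters excluded | Therapy start or death |
|---|---|---|---|---|
| 0 | -5.0 | -5.0 | -6.3 | -5.0 |
| 0.10 | -5.0 | -4.5 | -5.6 | -4.5 |
| 0.25 | -5.0 | -3.8 | -4.7 | -3.8 |
| 0.50 | -5.0 | -2.5 | -3.1 | -2.5 |

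The odds ratio hardly moves: 0.47 with all deaths counted, and 0.47 to 0.49 as written.

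*Unequal therapy start.* Let s be the share starting, with death risk d0 in non-starters and d1 in starters, the same in both arms. As written, the risk is (1 - s)d0. With all deaths counted it is (1 - s)d0 + s x d1. Take s = 20% v 30%, d0 = 2%, d1 = 15%.

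- As written: 0.8 x 2 = 1.6% v 0.7 x 2 = 1.4%, so +0.2 points.
- All deaths: 1.6 + 0.2 x 15 = 4.6% v 1.4 + 0.3 x 15 = 5.9%, so -1.3 points.

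Under this model, if more placebo patients start therapy and starters are at higher risk (d1 above d0), the two differences always have opposite signs. With equal s, both are 0.

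**The case against.** The strongest reply is that Table 22 is not ambiguous. Its row governs the derivation of death for this one estimand and so overrides the general rules, and the sentence after the population wording sends these medications to Table 22. Most of this stands: the non-event reading is the stated rule, and a reader should not infer that three readings are equally open. But that makes the rule itself the problem. It also leaves a gap, because a fatal-AE record is not plainly an assessment.

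A second reply is that the SAP truncates elsewhere: Table 20 does not consider deaths after study withdrawal unless consent is received to include them. The parallel is weak. A withdrawn patient is no longer observed, whereas a therapy starter remains in follow-up and the death is known.

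Third, labels do not control this SAP. Holding deaths at Day 28 is 'Composite variable' in Table 11 and 'Treatment policy' in Tables 12 and 13. This stands as far as it goes: the label alone changes no result. The discarding rule and the two censoring dates do.

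Fourth, Section 15 says only that therapy start may reflect lack of efficacy; it does not commit the sponsor to scoring it as failure. This also stands, so a true composite is one option and not a requirement.

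Two stronger inferences are tempting and unsupported. One is that Tables 16 and 19 also lose deaths; their Death rows prevent that. The other is that the trial's mortality result is compromised. The primary, ITT key secondary and first supportive analyses are untouched, the second supportive estimands are outside the testing hierarchy of Section 7.6, and the deaths remain visible in Table 20, for per-protocol patients in Table 21, and in the summary of TEAEs leading to death (Section 10.1).

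**Conclusion.** The point holds for the second supportive estimands only. In all five tables the 'Composite' label does not describe the rule. In Table 22 the rule scores a known death after therapy start as a non-event, contrary to Sections 5.3.1.5 and 7.3.1.1 and to the population wording. In Tables 10 and 13 one patient can have two censoring times. In Tables 16 and 19 the defect is limited to the label and the loss of non-fatal events after therapy start.

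The size cannot be determined from the documents. They give no death rate and no number of patients starting therapy on study; patients already on approved therapy at first dose are set to missing, so only later starters matter. The illustrations show how far the rule can depart from counting all deaths: 1.0 point in either direction with equal 10% mortality and a 35/25 split, and little change in the odds ratio when the share of deaths after therapy is equal across arms. They do not show that the rule favours either arm. No size is offered for Tables 10 and 13, because it would depend on unknown timing and on how prognosis relates to therapy use and death.

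**What to change.** 1. **Table 22.** Do not score a known death by Day 35 as a non-event. Either add a Death row that counts deaths from any Section 5.3.1.5 source regardless of therapy start, and relabel the therapy row 'Treatment policy'; or, if a composite is meant, define the event as therapy start or death and name the estimand accordingly.
2. **Tables 16 and 19.** Count therapy start as an event if a composite is meant. Otherwise relabel the row to describe the truncation. Leave the Death row as it is.
3. **Tables 10 and 13.** Either hold therapy starters at Day 28, a true composite that also removes the conflict with the Death row; or relabel the row 'Hypothetical' and censor every starter at therapy start whether or not they later die, with the Death row applying only to deaths before any therapy start. Do not combine the 'Hypothetical' label with precedence for the Death row: censoring at therapy start would then depend on a later death.
4. **Population sentences.** Align the wording about patients who do not receive such medication with the choice made.

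The cost is a few reworded rows in five tables, the matching sentences and a small derivation change; no new data are needed. One drawback: if all deaths count, Table 22 differs from Table 21 only in the prior-medication rule. The composite alternative keeps them distinct, but in the first assumed true-difference example (f = 0) it takes placebo from 10% to 30%, of which 20 points are therapy starts, so it is no longer an estimand of death.
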